neatid

The European treatment
network for HIV, hepatitis
and global infectious disease

STATISTICAL ANALYSIS PLAN

Protocol Title:	A MULTI-CENTRE, MULTI-COUNTRY RETROSPECTIVE COHORT STUDY TO EVALUATE THE CLINICAL OUTCOMES IN ADULTS WITH COVID-19 WHO HAVE BEEN TREATED WITH REMDESIVIR
SHORT TITLE/ACRONYM	909REM
SPONSOR NUMBER	NEAT ID 909REM
IRAS	293273
SAP VERSION	1.0
SAP VERSION DATE	07.05.2021

Prepared by Study Analyst:

Name: [name]

Date:

Signature:

DOCUMENT HISTORY

Document version number	Date	Reason for change

TABLE OF CONTENTS

1. ABBREVIATIONS AND DEFINITIONS	3
2. STATISTICAL HYPOTHESIS	4
3. STUDY OBJECTIVES AND ENDPOINTS.....	4
4. STUDY METHODS.....	5
4.1 GENERAL STUDY DESIGN AND PLAN	5
4.2 STUDY VARIABLES.....	6
5. SAMPLE SIZE CALCULATION	7
6. GENERAL CONSIDERATIONS.....	7
6.1 TIMING OF ANALYSES.....	7
6.2 ANALYSIS POPULATIONS	7
7. SUMMARY OF STUDY DATA	7
7.1 SUBJECT DISPOSITION	7
7.2 DEMOGRAPHIC AND BASELINE VARIABLES.....	7
8. EFFICACY ANALYSES.....	8
8.1 PRIMARY EFFICACY ANALYSIS.....	8
8.2 SECONDARY EFFICACY ANALYSES	8
9. OTHER ANALYSES	11
11. REPORTING CONVENTIONS.....	12
12. TECHNICAL DETAILS.....	12
APPENDIX.....	13
TABLE 1: BASELINE CHARACTERISTIC OF PARTICIPANTS AND ACCORDING TO THE DISEASE SEVERITY AT BASELINE.....	13
TABLE 2. PRIMARY AND SECONDARY OUTCOMES	16

1. Abbreviations and Definitions

Acronym	Description
ALT	Alanine Amino Transferase
AST	Aspartate aminotransferase
COPD	Chronic obstructive pulmonary disease
COVID	Coronavirus disease
CV	Cardiovascular
DM	Demographic
ECMO	Extracorporeal membrane oxygenation
e-CRF	Electronic Case Report Form
EMR	Electronic Medical Record
HIV	Human Immunodeficiency virus
ICU	Intensive Clinical Unit
ITU	Intensive Terminal Unit
NEAT ID	The European treatment network for HIV, hepatitis and global infectious diseases
NEWS	National Early Warning Score
NK	Not Known
ORDSC	Ordinal Scale Category
PCR	Polymerase Chain Reaction

2. Statistical hypothesis

There is no formal statistical hypothesis to be tested in these analyses. The study will explore the clinical course and outcome of adults with COVID-19 who have been treated with Remdesivir.

3. Study Objectives and Endpoints

Objectives	Endpoints
Primary	
All-cause mortality at Day 28	
 Occurrence of death (all cause) within 28 days

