6.2 Analysis Populations

All enrolled participants who met the eligibility criteria and with data available at baseline will be included in the Full Analysis Population. The primary endpoint and all secondary endpoints will be analysed on this Full Analysis population.

7. Summary of Study Data

All continuous variables will be summarized using the following descriptive statistics: n (non-missing sample size), mean, standard deviation, 1st quartile, median, 3rd quartile, maximum and minimum. The frequency and percentages (based on the non-missing sample size) of observed levels will be reported for all categorical variables.

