7.1 Subject Disposition

The number of patients and the flowchart of the study will be presented. The period of enrolment will be given. The number of patients excluded, and the total number of analysed patients will be presented. The number of patients who never take the study treatment will also be given. The number of patients who did not receive the full dose of Remdesivir will also be presented. The number of participants who discharge or die before day 28 will be presented.

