8.1 Primary Efficacy Analysis

Primary endpoint	
 Occurrence of death within 28 days
Analysis population	
 Full population analysis
Descriptive statistics and graphical representation	
 Data will be summarized with proportion and 95% confidence interval globally and according to disease severity at baseline (ORDSC score 2 vs 3-4 vs 5) LogRank test will be used to compared the 3 groups P-values will be two-tailed with a significant level at 5%. Kaplan-Meier curves will be plotted
Statistical analysis	
Kaplan-Meier estimates will be used to calculate the proportions and the 95% confidence intervals
 
Time to death will be defined as the time between the date of hospitalization and the date of death or discharge from hospital or last observation
 
Participant with missing clinical status or alive at day 28 will be censored at the date of last observation

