8.2 Secondary Efficacy Analyses

Endpoint	
 Disease state on a 7-point scale at Day 7, 14 and 28 (or last observation if discharged or died prior to this time point) defined as: 
 death, hospitalized, on invasive mechanical ventilation or ECMO, hospitalized, on non-invasive ventilation or high flow oxygen devices, Hospitalized, requiring low flow supplemental oxygen, hospitalized, not requiring supplemental oxygen - requiring ongoing medical care (COVID-19 related or otherwise), hospitalized, not requiring supplemental oxygen - no longer requires ongoing medical care, not hospitalized
----------	-------------------------------------------------------------------------------------------------------------------------------------------------------------------------------------------------------------------------------------------------------------------------------------------------------------------------------------------------------------------------------------------------------------------------------------------------------------------------------------------------------------------------------------------------------------------------------------------------------------------------------------------------------------------------------------------------------------------------------------

Analysis population	
 Full population analysis
Descriptive statistics and graphical representation	
 Data will be summarized with proportion and 95% confidence interval globally and according to disease severity at baseline (ORDSC score 2 vs 3-4 vs 5) Proportional odds models will be used to compared the 3 groups P-values will be two-tailed with a significant level at 5%.
Statistical analysis	
The proportions will be calculated by the number of subjects in each category divided by the total number of subjects in the full analysis population.
 
Subjects with missing clinical status will be considered deceased
 
The associated two-sided 95% exact confidence intervals will be calculated using Clopper–Pearson method

Endpoint	2. Disease severity at day 7, 14, and 28 as assessed by NEWS 2 score
Analysis population	
 Full population analysis

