Descriptive statistics and graphical representation	
 Data will be summarized with mean and 95% confidence interval globally and according to disease severity at baseline (ORDSC score 2 vs 3-4 vs 5) Linear mixed models will be used to compared the 3 groups P-values will be two-tailed with a significant level at 5%. The evolution curves will be plotted
Statistical analysis	
The changes from baseline in NEWS 2 score within group will be compared using mixed models for repeated measures with random intercept and unstructured covariance matrix, adjusted for baseline value. Subjects who die will be imputed as a score of 20 and subjects who are discharged will be imputed a score of 2. The sample size is quite large to consider the residuals of the mixed model is normally distributed. Time will be considered as categorical variable

Endpoints	3.1. Occurrence of SpO2 >94% on room air on day 7, 14 and 28 3.2. Time to SpO2 > 94% on room air
Analysis population	
 Full population analysis
Descriptive statistics and graphical representation	
 Data will be summarized with proportion and 95% confidence interval for the occurrence of SpO2 >94% on room air and median and 95% confidence interval for time to SpO2>94%. Data will be summarized globally and according to disease severity at baseline (ORDSC score 2 vs 3-4 vs 5)

	
 • LogRank test will be used to compared the 3 groups • P-values will be two-tailed with a significant level at 5% • Kaplan-Meier curves will be plotted
Statistical analysis	
Kaplan-Meier estimates will be used to calculate the proportion and the median time as well as the associated 95% confidence intervals
 
Time to event will be defined as the time between the date of first symptom and the date of the event of interest or hospital discharge or last observation
 
Subjects who died with $\text{SpO}_2 \leq 94\%$ will be censored at day 28

Endpoints	4.1. Frequency of oxygen therapy overall and by type (low versus high flow oxygen) 4.2. Duration (days) of oxygen therapy 5. Frequency of ICU admission 6. Number of days spent in ICU/ITU 7.1. Frequency of mechanical ventilation/ECMO of hospitalization 7.2. Time on mechanical ventilation/ECMO
Analysis population	
 • Full population analysis

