	Alert				
	Verbal				
	Pain				
	Unresponsive				

NEWS 2 score, median (IQR)						
	Low (score 0-4), n(%)					
	Medium (score 5-6)					
	High (score 7 or more)					
COVID Vaccination, n(%)						
Other treatment for COVID-19, n (%)						
	Corticosteroids					
	Tocilizimab/Sarilumab					
	Other COVID Treatment Related Drug					

Table 2. Primary and secondary outcomes

	Overall Total N=xxx	Ordinal Scale Category			
		Score of 2 N=xxx	Score of 3-4 N=xxx	Score of 5 N=xxx	P- value
Mortality over entire study period					
Number of deaths by Day 28					
Kaplan-Meier estimate of mortality by Day 28 – % (95% CI)					
Ordinal Scale at day 7 (± 1 day) – no. (%)					
1					
2					
3					
4					
5					
6					
7					
Ordinal Scale at day 14 (± 2 days) – no. (%)					
1					
2					
3					
4					
5					
6					
7					
Ordinal Scale at day 28 (± 2 days) – no. (%)					
1					
2					
3					
4					
5					
6					
7					
Disease severity assessed by NEWS 2 Score at 7 days					
Total N					
Mean NEWS 2 Score at days 7 (95% CI)					
Disease severity assessed by NEWS 2 Score at 14 days					
Total N					
Mean NEWS 2 Score at days 14 (95% CI)					
Disease severity assessed by NEWS 2 Score at 28 days					

Total N					
Mean NEWS 2 Score at days 28 (95% CI)					
SpO2>94% over first 7 days					
Number of SpO2>94% by Day 7					
Kaplan-Meier estimate of by Day 15 – % (95% CI)					
SpO2>94% over first 14 days					
Number of SpO2>94% by Day 14					
Kaplan-Meier estimate of SpO2>94 by Day 14 – % (95% CI)					
SpO2>94% over entire study period					
Number of SpO2>94% by Day 28					
Kaplan-Meier estimate of SpO2>94 by Day 28 – % (95% CI)					
Median time to SpO2>94% (95% CI) - days					
Oxygen therapy over entire study period (low or high flow)					
Number of oxygen therapy by Day 28					
Kaplan-Meier estimate of oxygen therapy by Day 28 – % (95% CI)					
Median duration on oxygen therapy (95% CI) - days					
Low flow oxygen therapy over entire study period					
Number of low flow oxygen therapy by Day 28					
Kaplan-Meier estimate of low flow oxygen therapy by Day 28 – % (95% CI)					
High flow oxygen therapy over entire study period					
Number of high flow oxygen therapy by Day 28					
Kaplan-Meier estimate of high flow oxygen therapy by Day 28 – % (95% CI)					
ICU admission over entire study period					
Number of ICU admission by Day 28					
Kaplan-Meier estimate of ICU admission by Day 28 – % (95% CI)					
Median duration spent in ICU (95% CI) - days					

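### SAP 8.2 scores missing clinical status as death on the ordinal scale, and Table 2 does not separate assumed from recorded deaths

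*SAP*

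**What the plan says.** SAP 8.2, endpoint 1, describes clinical status on a 7-point scale at Days 7, 14 and 28, with category 1 meaning death. Each proportion is taken over the whole full analysis population, with a Clopper-Pearson 95% interval. The three baseline severity groups (score 2, 3-4, 5) are compared by a proportional odds model. Two provisions deal with patients who lack a status at the visit:

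- Patients who have already left hospital or died are covered by the endpoint definition: "or last observation if discharged or died prior to this time point".
- For the rest: "Subjects with missing clinical status will be considered deceased".

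SAP 8.1, for death within 28 days, has a different rule: "Participant with missing clinical status or alive at day 28 will be censored at the date of last observation". Both analyses use the same patients (SAP 6.2): "The primary endpoint and all secondary endpoints will be analysed on this Full Analysis population".

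In the SAP Appendix, Table 2 has rows 1 to 7 for the ordinal scale at each of the three days, with no row for missing status and no note on imputation. A separate row, "Number of deaths by Day 28", exists for Day 28 only. The SAP gives no reason for counting missing as deceased and plans no sensitivity analysis around it.

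**The concern.** This is an explicit instruction. A programmer who follows it exactly will place patients with no recorded status in the row defined as death, and the table gives the reader no sign of it. The exact confidence interval will then treat assumed deaths as observed ones.

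The study is descriptive and covers treated patients only. SAP section 2 says: "There is no formal statistical hypothesis to be tested in these analyses". The value of the ordinal table therefore lies in how accurately it describes what happened. At stake is the published share of patients reported as dead at Days 7, 14 and 28, overall and by baseline severity.

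**Working it through.** The documents give no mortality rate, in-hospital share or missing-data rate, so there is no planned figure to reproduce. The check has four steps.

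**1. Whom the rule reaches.** Patients discharged or dead before the visit take their last observation. What remains is mainly patients not known to be discharged or dead who have no record in the window (±1 day at Day 7, ±2 days at Day 14). Many of these could still be in hospital.

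**2. Whether it can contradict the record.** Take a patient with no Day 7 status who is recorded in hospital at Day 14. Under the rule this patient is in category 1 at Day 7 and in one of categories 2 to 6 at Day 14: dead, then alive.

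**3. Size of the effect on category 1.** Let N be the analysis population, D the recorded deaths and m the number with missing status. Under SAP 8.2, category 1 = (D + m)/N. N = 450 is the planned minimum (Protocol 6.2, SAP section 5). D = 45 and all values of m are assumptions.

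| m | (D + m)/N | Category 1 (exact 95% CI) | Unverified share, m/(D + m) |
|---|---|---|---|
| 0 | 45/450 | 10.0% (7.4-13.2) | 0% |
| 7 | 52/450 | 11.6% (8.8-14.9) | 7/52 = 13% |
| 14 | 59/450 | 13.1% (10.1-16.6) | 14/59 = 24% |
| 23 | 68/450 | 15.1% (11.9-18.8) | 23/68 = 34% |

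The added percentage is m/450 whatever D is. With 9 missing it is 2.0 points: 23 recorded deaths go from 5.1% to 32/450 = 7.1%, and 68 go from 15.1% to 77/450 = 17.1%.

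How plausible m is depends on how many patients are still in hospital. If about 143 of 450 are, then 7, 14 and 23 missing are 4.9%, 9.8% and 16.1% of them. If only 50 are, 2, 5 or 10 missing patients give 47/450 = 10.4%, 50/450 = 11.1% and 55/450 = 12.2%. If half of the missing truly died, the overcount halves.

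**4. Effect on the proportional odds comparison.** The model was fitted by maximum likelihood to expected counts. All inputs are assumed:

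- groups of 45, 315 and 90 for scores 2, 3-4 and 5;
- score-5 group distributed 4/2/3/5/6/3/77% over categories 1 to 7;
- true odds ratios for worse status of 10 (score 2 vs 5) and 2.5 (3-4 vs 5);
- only categories 2 to 6 can be missing.

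| Missing among in-hospital patients, scores 2 / 3-4 / 5 | Missing as category 1 | Missing left out |
|---|---|---|
| 5/5/5% | 9.71, 2.50 | 10.17, 2.51 |
| 2/5/10% | 9.25, 2.46 | 10.58, 2.61 |
| 10/5/2% | 10.30, 2.51 | 9.94, 2.45 |
| 15/5/0% | 10.90, 2.52 | 9.78, 2.41 |
| 20/20/20% | 9.06, 2.49 | 10.77, 2.54 |

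Both approaches move the odds ratios modestly. In these scenarios leaving the missing out is nearer the assumed truth for score 2 vs 5, and the SAP rule is nearer for 3-4 vs 5. Neither is shown to be less biased.

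**The case against.** The best defence is that this is a prespecified worst-category rule. Even without a comparator, counting missing as worst guards against too favourable a picture of outcomes. Under the rule no status stays missing, so the lack of a missing row follows from it. That rationale is recognisable, although the SAP does not state it. It supports keeping a worst-category analysis. It does not support printing assumed deaths as deaths without a label.

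Several stronger readings are tempting, and the documents do not support them:

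- **That SAP 8.1 and 8.2 contradict each other.** A time-to-event endpoint and an ordinal endpoint may use different missing-data rules.
- **That recorded and assumed deaths can never be told apart.** At Day 28 a reader can roughly subtract "Number of deaths by Day 28" from category 1, visit-window effects and deaths after discharge aside. At Days 7 and 14 Table 2 has no death count. The Kaplan-Meier curves planned in SAP 8.1 give approximate mortality at those days, not counts.
- **That the imputed deaths spread to other outputs.** For NEWS 2 the SAP says "Subjects who die will be imputed as a score of 20 and subjects who are discharged will be imputed a score of 2", and for disposition "The number of participants who discharge or die before day 28 will be presented". Both read naturally as recorded deaths, and the missing-status rule sits in endpoint 1 only.
- **That the denominator is undefined.** SAP section 7 uses the non-missing sample in general, but endpoint 1 names the full analysis population, and the specific rule governs.
- **That the severity comparison is badly distorted.** Step 4 of the working does not show this.

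It also stands that the amount of missing status is unknown. With none missing, nothing changes.

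**Conclusion.** The point holds for the description of the ordinal scale. As written, category 1 at Days 7, 14 and 28 mixes recorded and assumed deaths without a label, and the rule can override evidence that a patient was alive. This is worth correcting before the analysis, but it does not threaten the primary result: the Kaplan-Meier mortality estimate follows SAP 8.1 and does not use the rule.

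The size cannot be fixed from the documents. If 45 of 450 die and 7 to 14 patients lack status, category 1 rises from 10.0% to between 11.6% and 13.1%. It rises less if fewer patients remain in hospital, or if some of the missing did die. The wording of the rule and of the table shell is certain; the number of patients affected is not. The case rests on the reported death counts, not on the odds ratios.

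**What to change.** In SAP 8.2, endpoint 1, and Table 2:

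- (a) Score category 1 only for a recorded death on or before the visit, carried forward to later visits, and never for a patient with later evidence of being alive.
- (b) Add a missing-status row to the Day 7, Day 14 and Day 28 ordinal blocks of Table 2, keeping the full analysis population as the stated denominator.
- (c) Report the proportional odds comparison twice: with missing as the worst category, labelled as such, and on observed status. Do not claim that either is less biased.

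The cost is three table rows and one additional model. The dates of death and discharge that this needs are already used in SAP 8.1 and in endpoint 8 of SAP 8.2. The worst-category analysis is kept.

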2.2 Secondary objectives

The secondary objectives are to assess the clinical course and outcome of adults with COVID-19 who have been treated with Remdesivir with respect to the following:

1. a 7-point ordinal clinical status scale on Day 7 and Day 14
2. timing (from first symptoms and from hospitalisation) and duration of use of Remdesivir
3. clinical severity at Day 7, 14, 28 as assessed by the NEWS 2 score
4. clinical status as assessed a 7-point ordinal scale on Day 28 (or at last observation if discharged or died prior to this time point) in those still hospitalised after Day 14.
5. SpO₂ > 94% on room air on day 7, 14 and 28
6. duration and type (low versus high flow) of oxygen therapy (days)
7. admitted to ICU (yes versus no)
8. number of days spent on ICU/ITU
9. use of mechanical ventilation/ECMO (extracorporeal membrane oxygenation); start and stop dates
10. re-admission with COVID-19 complications or recurrence within 28 days of discharge and outcome (discharged or deceased)

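### SAP endpoint 3.1 is SpO2 above 94% on room air on Days 7, 14 and 28, but the plan estimates it only as a Kaplan-Meier cumulative proportion by each day, so on-day status is never reported

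*SAP*

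**What the plan says.** The protocol's secondary objective (2.2, item 5) is "SpO₂ > 94% on room air on day 7, 14 and 28". The SAP carries this over as "3.1. Occurrence of SpO2 >94% on room air on day 7, 14 and 28" and lists a second endpoint beside it, "3.2. Time to SpO2 > 94% on room air". The second corresponds to protocol 2.4, item 5, where the evaluation criterion is the time to reach the target, evaluated on Day 7, 14 or 28.

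SAP 8.2 treats 3.1 and 3.2 in one box with one method:

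- Estimator: "Kaplan-Meier estimates will be used to calculate the proportion and the median time as well as the associated 95% confidence intervals", with a log-rank test across the three baseline severity groups.
- Clock: "Time to event will be defined as the time between the date of first symptom and the date of the event of interest", with discharge or last observation as the alternative end.
- Deaths: "Subjects who died with $\text{SpO}_2 \leq 94\%$ will be censored at day 28".

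Table 2 in the SAP Appendix has three SpO2 blocks. The middle one is headed "SpO2>94% over first 14 days" and its count row reads "Number of SpO2>94% by Day 14". The other two have the same form for 7 days and for the entire study period. Each block has a Kaplan-Meier percentage row. No row gives the number of patients at target on a given day.

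**The concern.** Being at the target on Day 14 and having reached it at some time up to Day 14 are different quantities. The first can go down between visits as patients deteriorate. The second cannot. The SAP names both, as 3.1 and 3.2, but plans an estimator for the second only.

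As a result, the Day 14 and Day 28 oxygenation figures cannot show a surviving patient's return to oxygen or ventilation after an earlier good reading, and the objective in protocol 2.2, item 5 is not answered. Table 2 would also be hard to read across. A patient on high-flow oxygen on Day 14 falls in category 3 of the Day 14 ordinal block and, if at target on Day 7, is also counted in the Day 14 SpO2 block.

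**Working it through.** The plan states no SpO2 rate and no sample size calculation, so there is no figure of its own to reproduce. The check is one of definition, followed by an illustration on assumed rates.

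**1. The two quantities.** Let T be the time at which the target is first reached.

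- Kaplan-Meier by day t estimates P(T ≤ t), which cannot decrease in t.
- Endpoint 3.1 is P(alive, SpO2 above 94% and on room air on day t), which can decrease.
- On a common clock, with no censoring before the event, gap = P(T ≤ t) × P(not at target on day t, given T ≤ t) ≥ 0.

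**2. Which days are affected.** SAP 4.2 schedules SpO2 on Day 1 (admission), Day 7, Day 14 and Day 28, or at last observation. If only scheduled post-baseline readings can be the event, Day 7 is the first opportunity, so the two quantities coincide there and can differ only at Days 14 and 28. Day 7 is affected too if a Day 1 or between-visit reading can be the event. The SAP does not say.

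**3. Size at Day 14, assumed rates.** N = 450 is the planned minimum. Assume 50-70% reach the target by Day 7 and 5-20% of those are not at target on Day 14.

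- Low: 450 × 0.50 × 0.05 = 11.25, about 11 patients; 0.50 × 0.05 = 2.5 points.
- High: 450 × 0.70 × 0.20 = 63 patients; 0.70 × 0.20 = 14 points.

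**4. Size at Day 28, assumed rates.** Assume 60-80% ever reach the target and 5-20% of those are not at target on Day 28.

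- Low: 450 × 0.60 × 0.05 = 13.5 patients, 3 points.
- High: 450 × 0.80 × 0.20 = 72 patients, 16 points.

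For comparison, the 95% Clopper-Pearson half-width at N = 450 is 4.6 points for a proportion of 60%, 4.3 for 70% and 3.8 for 80%. The gap could therefore be smaller or larger than the reported uncertainty.

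**5. Worked cohort of 450 (invented counts).** Scheduled visits only, one clock, and patients who die without reaching the target stay at risk to Day 28, as the SAP's death rule implies. First attainments are 220 at Day 7, 105 at Day 14 and 50 at Day 28.

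| Day | Reached by day (Kaplan-Meier) | At target on day | 95% CI, on-day |
|---|---|---|---|
| 7 | 220/450 = 48.9% | 220/450 = 48.9% | 44.2-53.6% |
| 14 | 325/450 = 72.2% | 290/450 = 64.4% | 59.8-68.9% |
| 28 | 375/450 = 83.3% | 335/450 = 74.4% | 70.2-78.4% |

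Of the 375 − 335 = 40 patients behind the Day 28 gap, 20 had died and 20 were alive but off target. The survivors alone account for 20/450 = 4.4 points.

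**6. The clock.** Day 1 is admission, but Kaplan-Meier time starts at first symptom. If symptoms began s days before admission, the Day d visit falls at s + d − 1 days on the Kaplan-Meier clock. With s = 7 (assumed), the Day 7 visit falls at 7 + 7 − 1 = 13 days, so it cannot contribute to a Kaplan-Meier figure at 7 days. This pulls the cumulative figure down, while step 1 pushes it up. The documents do not allow the net effect to be worked out.

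**7. How the SAP treats another fixed-day endpoint.** For the ordinal scale on the same three days, SAP 8.2 divides the number in each category by the full analysis population and uses Clopper-Pearson intervals, with death as a category. That method lets later deterioration show.

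**The case against.** The strongest reply is that the protocol itself asks for a time-to-event analysis. Protocol 2.4, item 5 makes time to the target the evaluation criterion, and Kaplan-Meier serves that. This stands, and it means the SAP did not simply depart from the protocol, whose objective and criterion differ from each other. It justifies Kaplan-Meier for 3.2. It does not cover 3.1, which the SAP defines separately to match the objective.

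Three stronger readings are tempting, and the documents do not support them.

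- **That a patient admitted at 96% on room air, then ventilated and dead by Day 14, counts as a success on all three days.** This needs the Day 1 reading to be an event. Nothing says that it is, and protocol 2.4, item 5 ties the evaluation to Days 7, 14 and 28.
- **That deaths after an earlier success certainly count as successes.** The death rule can be read as applying to SpO2 at the time of death, which would override an earlier success. It can also be read as covering only patients who never reached the target. On the first reading only the death part weakens; survivors who lose the target are still counted.
- **That the reported figures overstate recovery.** This holds only on a common clock, and the SAP's two clocks differ.

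It is also fair to say that the SAP never uses the words first or ever. That meaning follows from a standard single-event Kaplan-Meier analysis and from the cumulative labels in Table 2. Finally, deterioration and death are visible elsewhere in Table 2 (mortality, ordinal scale, NEWS 2, ventilation), the SpO2 rows are openly labelled as cumulative, and the study tests no formal hypothesis. This limits the consequence but does not supply the missing endpoint.

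**Conclusion.** The mismatch is in the text. Endpoint 3.1 is a status on Days 7, 14 and 28, the only planned estimates are cumulative, and no Table 2 row reports the endpoint as defined. Survivors who lose the target after reaching it remain counted at Days 14 and 28. Day 7 is affected only if a Day 1 or between-visit reading can be the event, and the treatment of deaths after an earlier success is unclear.

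The size cannot be taken from the documents. On a common clock the cumulative figure is at or above the on-day figure. The ranges of 11 to 63 of 450 patients at Day 14 and 3 to 16 points at Day 28 rest wholly on assumed rates and illustrate what is possible. A reader might infer a bias of that size in favour of recovery. The documents do not establish this, because the symptom-based clock can act in the opposite direction.

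This is a secondary, descriptive endpoint, so the matter is one that should be corrected rather than one that undermines the study.

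**What to change.** Split the shared box in SAP 8.2.

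- **Endpoint 3.1.** Report n (%) alive with SpO2 above 94% on room air in each of the Day 7, 14 and 28 windows, using the last observation for patients discharged earlier. The denominator is the full analysis population and the intervals are Clopper-Pearson, as for the ordinal scale. Count deaths and patients on any oxygen support as not meeting the endpoint, and state a rule for missing readings.
- **Group comparison for 3.1.** Replace the log-rank test with a test for proportions, such as the chi-square test that the SAP already uses for readmission.
- **Endpoint 3.2.** Keep Kaplan-Meier and the log-rank test here only. State which readings can be the event, and whether the death rule applies to patients who reached the target earlier.
- **Table 2.** Change the three cumulative SpO2 blocks to on-day rows, with room air in the label. The Kaplan-Meier row in the 7-day block is labelled Day 15; the mislabelled row goes in the same edit.

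The cost is minor rewording of one box and three table blocks. No new data are needed, because SpO2 and oxygen support are already scheduled at every visit. The downside is that the percentages may look less favourable.
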